#### 8.12.1.2 Safety laboratory

Laboratory values will be graded by NCI CTCAE version 4.03; if no grading exists values will be classified into low/normal/high based on laboratory normal ranges. Each parameter will be presented by descriptive statistics at each visit and change from baseline values at each visit. Shift tables for CTCAE grades and normal ranges will be presented. All laboratory values will be listed. A separate listing for abnormal lab values (Grade 3 and higher, and low/high values) will be presented.

#### 8.12.1.3 Vital signs

Vital signs will be summarized by descriptive statistics at each visit, change from baseline will be presented and a listing will be provided.

#### 8.12.1.4 Electrocardiogram

ECG data will be listed overall and a separate listing for any clinical significant finding in ECG values will be provided.

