- Alternatively, 2 core needle (fresh tumor) biopsies or a single newly obtained excisional biopsy sample can be submitted (processed into one FFPE block), together with either an archival (FFPE) tumor tissue block or a minimum of 10 unstained slides each 5 $\mu$ m cut from the archival tumor sample block. The unstained slides must arrive at the testing laboratory within 14 days. In this option, an archival FFPE block is strongly preferred over unstained slides cut from an archival FFPE block.

Archival blocks must be clearly labelled as archival.

Slides cut from an archival tissue block must be clearly marked as having come from an archival block.

Finally, where patients also have (additional) archived biopsy material which is suitable for additional (such as exploratory) biomarker assessment a sample of this material (either as an archival FFPE block or slides cut (and paraffin dipped) from the archival block) can also be prepared for study biomarker assessment. The patient will be offered a separate optional patient consent to enable this 'archival biomarker tumor sample' to be submitted.

The first dose of study drug must be administered within 4 weeks of commencing the Screening assessments. Tumor imaging by computed tomography (CT) or magnetic resonance imaging (MRI) of the chest, abdomen and pelvis is required during the Screening period. X-ray scans can be used where appropriate (for example, for symptomatic sites that are negative on a bone scan). All patients should undergo a bone scan and a brain scan in the 6 weeks prior to starting treatment.

Recording of AEs and concomitant medications, plus laboratory screens including electrocardiographs (ECGs) will be performed at each study visit. During Cycle 1, patients will have study visits on Days 1, 2, 3 and 4, then on Days 8 and 15. From Cycle 2, Day 1, study visits will be reduced to every 3 weeks.

ECG assessments will be performed in triplicate at pre-dose and 6 hours after the BGB324 dose on Day 1, Cycle 1 and then repeated pre-BGB324 dose on Days 2, 3 and 4 (Cycle 1) and then at every visit thereafter.

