- 8 Fresh tumor tissue from all patients at Screening is mandatory, and optional at up to 2 time points during participation in the clinical trial ('on-study' biopsy). Where possible, these optional samples should be taken at the point of tumor response or progression. Suitable archival biopsy material may also be obtained at Screening. Please refer to protocol [Section 5.3.13](#), the Laboratory or Pathology Manual for full details on biopsy sample collection, time-points, processing, storage and shipment. If a patient discontinues BGB324 (but continues pembrolizumab), there is no requirement for the optional 'on study' biopsy.
- 9 Blood samples will be collected at Screening (or D1 pre-dose), D4, D8, then at every study visit up to and including C9 D1 to prepare PBMC and serum samples for Axl signaling and inhibition biomarker assessment. Please refer to the Laboratory Manual for full details on biomarker sample collection, time-points, processing, storage and shipment. If a patient discontinues BGB324 (but continues pembrolizumab), there is no requirement for biomarker blood samples.
- 10 Pembrolizumab dose of 200 mg will be administered every 3 weeks (timing window +/- 3 days). Each dose will be infused over 30 minutes (timing window -5/+10 minutes)
- 11 BGB324 will be taken orally once daily. On visits when pembrolizumab and BGB324 are given on the same day, pembrolizumab must be given first and the patient observed for 1 h prior to administration of BGB324.
- 12 a) The maximum PK sampling time points for the measurement of BGB324 in blood will be: C1 D1 pre-dose, 2, 4, 6, 8 hours ; D2 pre-dose; D3 pre-dose, 2, 4, 6, 8 hours; D4 pre-dose; and then pre-dose at C1D8, C1D15, C2D1 and then C3D1. Samples should be taken contemporaneously with the ECG assessments on C1 D1-4. All sample times are approximate but every effort must be made to take PK samples at specified times.

- b) The maximum PK sampling time points for the measurement of pembrolizumab in blood will be: C1 D1 pre-dose; D2; D3; D4; and then at C1D8, C1D15; C2D1 pre-pembro dose and then C3D1 pre-pembro dose. All sample times are approximate but every effort must be made to take PK samples at specified times

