### 5.3.9 Electrocardiogram

A resting 12-lead ECG will be performed at the times given Schedule of Study Assessment [Table 4](#) and [Table 5](#). Each assessment time point must be performed in triplicate.

All 12-lead ECGs should be recorded while the patient is in the supine position. ECGs will be recorded at 25 mm/sec. All efforts should be made to ensure that an identical ECG machine is used to collect traces for individual patients. The Investigator or designated physician will review the ECG results.

If any clinically significant findings are observed on the ECG, the Investigator will record it as part of the medical history prior to the start of dosing, and as an AE post dose where the finding represents a change from baseline. Clinically significant findings identified prior to start of dosing must be checked against the study exclusion criteria ([Section 3.2](#)). Note that the average value of the three assessments performed at each time point should be applied, except at Screening, where both the Screening and pre-dose Cycle 1 Day 1 assessments should be combined. Patients may be excluded based on the initial triplicate assessment at Screening.

Patients who discontinue BGB324, but continue with monotherapy pembrolizumab will stop undergoing an ECG.

Patients who have a BGB324 interruption of 14 days for toxicity (see [Table 12](#) and [Table 13](#)) will require an ECG twice weekly for the 2 weeks following recommencement of BGB324 daily dosing. This is to ensure cardiac safety monitoring whilst BGB324 returns to steady state.

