### 6.6.2 BGB324 dose modification for QTc

Treatment with BGB324 produces QTc prolongation. In order to reduce the risk of QTc prolongation, all efforts should be made to maintain the patient's serum potassium levels at  $>4$  mmol/L during treatment with BGB324 and for 2 weeks following completion of therapy (at an unscheduled visit, if required). Serum calcium and magnesium should be measured and reasonable efforts made to maintain at normal levels throughout treatment. Patients with an average QTc of  $\geq 480$  ms should be closely monitored until the QTc falls below 480 ms; electrolytes should be measured and corrected as necessary.

If a patient experiences QTc prolongation, BGB324 dosing should be reduced as outlined in [Table 13](#). **Treatment with BGB324 should be permanently discontinued in the presence of ventricular arrhythmia.**

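### Section 8.12.1.4 plans only listings for measured ECG values, although BGB324 is stated to prolong QTc and the other measured safety parameters are summarised by visit

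*Protocol*

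**What the plan says.** **ECG analysis.** Protocol Section 8.12.1.4 consists of one sentence: "ECG data will be listed overall and a separate listing for any clinical significant finding in ECG values will be provided". It mentions no descriptive statistics, change from baseline or table of QTcF categories.

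**The neighbouring paragraphs.** Section 8.12.1.2 says of laboratory values: "Each parameter will be presented by descriptive statistics at each visit and change from baseline values at each visit". It adds shift tables by CTCAE grade and normal range, and listings. Section 8.12.1.3 says: "Vital signs will be summarized by descriptive statistics at each visit, change from baseline will be presented and a listing will be provided".

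**The endpoint.** Tables 1 and 9 put laboratory parameters, vital signs and ECGs side by side in the secondary safety endpoint.

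**Why QTcF matters here.** Section 6.6.2 states: "Treatment with BGB324 produces QTc prolongation". Exclusion criterion 9 bars a screening QTcF above 450 ms. Table 13 sets BGB324 interruption, reduction and discontinuation by QTcF grade, using the mean of the triplicate readings.

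**Collection.** The synopsis schedules ECGs pre-dose and 6 hours post-dose on Cycle 1 Day 1, pre-dose on Days 2, 3 and 4, "and then at every visit thereafter". Section 5.3.9 adds: "Each assessment time point must be performed in triplicate". The same section ends ECGs for patients who stop BGB324 and continue on pembrolizumab.

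**Route to the adverse event tables.** Under Section 5.3.9, a clinically significant post-dose ECG finding that is a change from baseline is recorded as an adverse event. Section 8.12.1.1 tabulates adverse events by preferred term, grade, interruption, discontinuation and other headings.

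**The concern.** The three measured safety parameters share one endpoint. The one with a stated drug effect has the weakest planned analysis. A listing lets a reader look up one patient's values. It does not give the average QTcF change after the loading dose or at steady state, or the number of patients who moved into each grade band.

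The adverse event tables depend on a judgement of clinical significance. Table 13 requires no dose change at 450-480 ms. At 481-500 ms it acts on two consecutive occasions or on the investigator's judgement. A consistent moderate shift across many patients could therefore produce few adverse events and stay invisible in the tables. For a first combination of these two drugs, that shift is a basic result of the safety objective.

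**Working it through.** No design figure is at issue, so there is none to reproduce. The check compares the analysis paragraphs and then counts the data concerned.

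**1. Planned output for each part of the safety endpoint**

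| Parameter | Section | Statistics by visit | Change from baseline | Shift or category table | Listing |
|---|---|---|---|---|---|
| Laboratory | 8.12.1.2 | yes | yes | yes | yes |
| Vital signs | 8.12.1.3 | yes | yes | not stated | yes |
| ECG | 8.12.1.4 | not stated | not stated | not stated | yes (two) |
| Adverse events, including ECG findings reported as such | 8.12.1.1 | not applicable | not applicable | contingency tables | yes |

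**2. What the adverse event route leaves out**

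A QTcF value reaches a table only if it is judged clinically significant, is a change from baseline and is recorded as an adverse event. Values that fail the first test appear in the overall listing alone. Readings of 450-480 ms, where Table 13 asks for no dose change, are the obvious candidates.

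**3. ECG time points per patient** (Table 4, Table 5 and footnote 6; Section 5.1.1)

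- Screening: 1
- Cycle 1 Day 1, pre-dose and 6 hours: 2
- Cycle 1 Days 2, 3, 4, 8 and 15: 5
- Cycles 2 to 35, Day 1: 34
- Post Treatment Visit: 1

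Full course: 1 + 2 + 5 + 34 + 1 = 43 time points. In triplicate, 43 × 3 = 129 tracings per patient, and 129 × 56 = 7,224 for 56 patients.

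Through Cycle 8, the last cycle starting within the 24-week follow-up: 1 + 2 + 5 + 7 = 15 time points. That is 15 × 3 = 45 tracings per patient and 45 × 56 = 2,520 for 56 patients.

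Both totals are maxima that ignore early discontinuation. Cycles 1 and 2 alone contribute 8 time points, or 9 with screening.

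**4. What a category table could show**

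If none of n patients crosses a limit, the one-sided 95% upper bound for the true share is 1 − 0.05^(1/n). For n = 28 this is 10.1%; for n = 56 it is 5.2%. If 6 of 56 cross, the exact two-sided 95% interval is 4.0% to 21.9%. These are modest but useful statements, and listings provide none of them.

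**5. Paired ECG and PK times**

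Footnote 12 to the schedule says: "Samples should be taken contemporaneously with the ECG assessments on C1 D1-4". On those days the ECG times are Day 1 pre-dose, Day 1 at 6 hours, and pre-dose on Days 2, 3 and 4. That gives five pairs per patient, one of them before any drug. Nominal times also coincide at Days 8 and 15 and at Day 1 of Cycles 2 and 3, giving nine in all. An exploratory plot is feasible, but the data are sparse.

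**The case against.** The strongest objection is that Section 8.3 describes the main analyses only briefly and leaves full detail to the SAP. Section 8.12.1.4 promises listings without excluding tables, so a SAP that added QTcF tables would contradict nothing. This stands in part: the SAP is not shown, and it may already contain them. But the protocol is not silent here. It names a method for ECG that is weaker than the methods it names for the two comparable parameters. Whatever the SAP says, the sentence is worth bringing into line.

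The second objection is that QTc safety is covered elsewhere. Reported events are tabulated, reasons for discontinuation are summarised (Section 8.10), the Data Review Committee sees ECG results at the run-in reviews (Section 4.1), and Table 13 governs individual patients whatever the report contains. All of this is correct. A reader might infer from Section 8.12.1.4 that the QTc risk gets no summary at all, and that is not so. What lacks a summary is the measured values.

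Three further inferences go beyond the documents:

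- **That QTc prolongation is the main known risk.** The protocol states the effect but does not rank it. Section 1.4.1 names gastrointestinal disorders as the most common related events.
- **That the paired ECG and PK data will go unused.** Section 8.12.3 leaves the BGB324 PK analysis plan to the SAP, so this cannot be known. Tables 1 and 9 also set no objective relating concentration to QTc.
- **That the protocol implies limits on the size of change, such as 30 or 60 ms.** It gives none. Its own limits are the absolute grades in Table 13.

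**Conclusion.** The point holds for measured ECG values. As written, the protocol would report QTcF through two listings, while laboratory values and vital signs are summarised by visit with change from baseline. Only QTc events reported as adverse events would reach a table. The mean QTcF shift, and the share of patients in each Table 13 band, would not be reported.

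This affects the completeness of a secondary safety endpoint. The primary endpoint, error rates, interim rule and individual dosing decisions are untouched. The data concerned are up to 15 time points per patient through Cycle 8 and 43 over a full course, fewer for anyone who stops BGB324 early.

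The conclusion assumes that Section 8.12.1.4 describes the intended ECG output. If the SAP already provides QTcF tables, what remains is a wording mismatch between the two documents.

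**What to change.** In Section 8.12.1.4, keep the two listings and add:

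1. Descriptive statistics for triplicate-mean QTcF and its change from baseline at each scheduled time point, including 6 hours post-dose on Cycle 1 Day 1. State which value is the baseline, given that Section 5.3.9 combines the Screening and Cycle 1 Day 1 pre-dose readings.
2. A shift table from baseline to worst on-treatment QTcF category, using the Table 13 bands (450-480, 481-500 and 501 ms or more) and a category below them.
3. Optionally, and labelled exploratory, a plot of QTcF change against time-matched BGB324 concentration.

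Use the same wording in the SAP.

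The cost is the programming of two tables, and one figure if wanted, from data already collected. No visit, sample, sample-size figure or dosing rule changes.

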### 8.12.2 Efficacy

#### 8.12.2.1 Duration of response

The duration of response (DoR) will only be calculated for patients that have an objective response. The duration of response is calculated from the date of the first documented response until the date of progression or death; patients who continue to respond at the date of data cut-off (last patient last visit) will be censored using the same date used to censor for the progression free survival time. Median DoR and respective 95% CIs will be presented.

### 8.12.2.2 Disease control rate

Disease control rate (DCR) is defined as the percentage of patients with a PR, CR or with stable disease (out of number evaluable). A 95% CI for the DCR will be calculated using an exact binomial distribution.

A Kaplan Meier plot of the duration of response will be presented along with the median duration of response. Descriptive statistics will be used as required, including 95% CIs.

### 8.12.2.3 Progression free survival and overall survival

Kaplan Meier plots of the time to progression and death will be presented, along with the median progression free survival and the estimated survival at 12 months. Descriptive statistics will be used as required, including 95% CI.

PFS is measured from the date of the 1st dose of the 1st cycle until the date of progression (the date on which the progression is initially observed) or the date of death (whichever is earlier). Patients who have not progressed or died before the date of data cut-off (last patient, last visit) will be censored at their last clinical evaluation.

The estimated survival at 12 months will be read from the Kaplan Meier OS curve. The time to death is defined as the time from the date of enrolment until the date of death (from any cause and irrespective of any subsequent ant-cancer treatment given). Patients who remain known to be alive at the date of data cut-off (last patient, last visit) will be censored at their date last known to be alive. Patients who are lost to follow-up will be censored at the point last known to be alive; however, if  $\geq 2\%$  of patients are in this category, a sensitivity summary will be produced to illustrate the overall survival assuming the patient died at the date last known in the trial. If possible, the date of death may be recovered from publically available sources such as death registries.

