### Number of Patients:

Up to 56 evaluable patients will be enrolled into the study. Approximately 75 patients will be screened in order to identify up to 56 patients who meet all the inclusion and exclusion criteria and are evaluable for response. This assumes a 25% screen failure rate, given the need for patients to provide a fresh tissue biopsy sample.

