## 5 STUDY SCHEDULE

The study consists of a Screening period, Treatment period, Post Treatment Visit and Follow-up period. Patients will attend the clinic for Screening period assessments up to 28 days before receiving the first dose of study treatment. The Post Treatment Visit will occur 30 days after the patient has discontinued both study treatments. All patients will continue in follow-up visits and continue to have their disease assessed and scanned (unless progression of disease has already been confirmed) and for survival status.

The study schedule will continue in keeping with the Study Assessment calendar. Patients will be required to visit the study sites for each study visit (which includes each pembrolizumab dose). From Cycle 2 onwards, a tolerance window of +/- 3 days is permitted. Pembrolizumab that cannot be given within these tolerance windows will be treated as a missed dose, although it is acceptable to have a pembrolizumab dose interruption for up to 3 weeks (for reasons other than toxicity). See [Section 6.6.3](#) for full details on pembrolizumab dose interruptions, including the duration of interruption for toxicity.

It is important that the calendar schedule for tumor assessment relative to Cycle 1, Day 1 is maintained (subject to permitted tolerance windows). If treatment administration is misaligned with weeks (e.g. because of treatment delay), the tumor assessment schedule should be maintained by week number ([Table 3](#), [Table 4](#) and [Table 5](#)). The schedule of disease assessment is every 12 weeks once a patient has stopped one or both or completed their (combination) treatment in the absence of progression.

Assessments requiring specific timing relative to the BGB324 or pembrolizumab dose are described in the footnotes to Schedule of Study Assessment [Table 4](#) and [Table 5](#).

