## 6.5 Method of Enrolling Patient to Study Treatment

During Screening, patients will be allocated a unique patient number from the RAVE, once written informed consent has been obtained. Patients will continue to be identified by this number throughout the study. Once a Subject Number has been assigned, it cannot be used again.

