#### 8.4 Population

The efficacy objectives will include all evaluable patients. An evaluable patient will have received at least one combination dose and who have measurable disease at entry according to the Investigator Site assessment.

For all safety objectives, the safety set consisting of all patients that have received at least one dose of BGB324 and/or pembrolizumab will be used.

For some objectives (PK and biomarker) a subgroup of patients of the safety set with respective baseline and post-baseline measurements will be used.

Patients who signed a consent form and were screened but did not receive any treatment will be listed if they reported an AE in the time after consent and before treatment allocation ([Section 7.1](#)). All AEs that occur after the consent form is signed but before treatment allocation must be reported if they cause the patient to be excluded from the trial, or are result of protocol-specific intervention, including but not limited to, washout or discontinuation of usual therapy, diet, placebo treatment or a procedure ([Section 7.1](#)).

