## 8.6 Completion and Closure of the Study

The study will be completed when either:

- The study is terminated at the interim analysis following the DRC review of the ORR and risk/benefit for all patients included in the interim analysis. In this (early termination) situation a Clinical Study Report will be written. The interim analysis will occur once 28 evaluable patients have had the potential to be followed for at

least 24 weeks. In this situation, the last patient, last visit (LPLV) will occur at this point.

*OR*

- The study will complete and the final analysis will occur once all patients (planned 56 evaluable patients) have had the potential to be followed for at least 24 weeks. The last patient, last visit (LPLV) will occur at this point. All data will be reconciled and the database will be locked for analysis. These data will be included in the CSR.

Assuming that there are patients continuing on study treatment at the date of LPLV, the study will be closed once all patients have completed their last dose of study drug or discontinued study drug and have completed their post treatment visit.

- If this closure date occurs after the date of LPLV, only serious safety data will be collected between LPLV and the final closure date. An addendum (or addenda) to the CSR will be generated to report any outstanding serious safety data.
- If this ‘closure date’ occurs before the date of LPLV (because every patient has stopped their study treatment, for example), the study will close at the same time as the date of LPLV.

Study start is defined by the first patient to enter screening, however, the First Patient In (FPI) is when the first patient receives the first dose of study drug.

LPLV is defined as the last visit after all evaluable patients who have had the potential to be followed for at least 24 weeks and includes all data for the final analysis of all evaluable patients.

Study Completion is defined by the date of the LPLV i.e. after the planned number of evaluable patients have had the potential to be followed for at least 24 weeks.

Study Closure is defined by completion of the last dose of study drug and post treatment visit i.e. when the last patient has completed the last dose of study drug or discontinued for any reason and been followed up to the Post Treatment Visit. This date will either be the same as the date of Study Completion or later in time.

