- ii. A separate Optional Consent for the provision of a baseline archival tumor tissue sample for the purpose of exploratory biomarker analysis will be presented to the patient.

During the trial, patients may be offered a further consent to provide an optional newly acquired tumor tissue sample for exploratory biomarker assessment.

The patient must give consent (the Main Consent form) to participate prior to enrolment in the trial. This consent must be given in writing. The Investigator who conducts the informed consent discussion must also sign. The Investigator may delegate this responsibility to a suitably qualified member of the study team (e.g. Sub-Investigator) if permitted by local regulations. This delegation of responsibility must be recorded in the Site Study File. By giving signed consent, the patient will confirm that his or her participation is voluntary and that he or she will follow the instructions of the Investigator and answer the questions asked. Signatures must be personally dated.

The signed and dated consent form(s) will be kept by the Investigator. Prior to participation in the trial, the patient should receive a copy of the signed and dated written informed consent form(s).

The consent forms must include all elements required by law, local regulations, GCP and ICH guidelines including consent to allow the Sponsor, Sponsor representative, or external regulatory auditor to review the patient's medical records. This gives permission to examine, analyse, verify, and reproduce any records and reports that are important to the evaluation of the trial.

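### Overall survival is timed from an undated enrolment while PFS starts at first dose, so 12-month OS may include a short stretch of guaranteed survival (minor)

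*Protocol*

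**What the plan says.** Section 8.12.2.3 gives two time origins. PFS runs from the first dose of the first cycle. For OS, "The time to death is defined as the time from the date of enrolment until the date of death". Survival at 12 months is then read from the Kaplan-Meier OS curve. Table 9 lists 12-month OS as a secondary endpoint, and Section 8.3 counts OS among the efficacy endpoints.

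No section attaches a date to enrolment. The places that bear on it are these:

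- Section 6.5, whose heading concerns enrolling the patient to study treatment: "During Screening, patients will be allocated a unique patient number from the RAVE, once written informed consent has been obtained".
- Section 10.3: "The patient must give consent (the Main Consent form) to participate prior to enrolment in the trial".
- Synopsis, Number of Patients: "Approximately 75 patients will be screened in order to identify up to 56 patients who meet all the inclusion and exclusion criteria".
- Section 8.2.1 equates six weeks of potential follow-up of enrolled patients with two treatment cycles.
- Section 8.6 separates study start (first patient entering screening) from First Patient In: "the First Patient In (FPI) is when the first patient receives the first dose of study drug".

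On the gap and the analysis set, Section 5 says "Patients will attend the clinic for Screening period assessments up to 28 days before receiving the first dose of study treatment", the synopsis says "The first dose of study drug must be administered within 4 weeks of commencing the Screening assessments", and Section 8.4 says "An evaluable patient will have received at least one combination dose".

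**The concern.** Patients enter the efficacy set only by being dosed, so each of them was alive at first dose. If the OS clock starts earlier, the time between the two dates carries no risk of death for anyone analysed. This is immortal time, and it moves the estimate in one direction only: 12-month survival from enrolment is really survival to 12 months minus the gap, counted from first dose.

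In a randomised trial a shared offset would largely cancel. Here there is no control arm, so it would stay in the reported figure, and a confidence interval would not show it. Two analysts could follow the text faithfully and report different 12-month values from the same data. A patient who dies without progression would also have one event but two durations, one for PFS and one for OS.

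**Working it through.** **The plan's own figures.** The protocol states no precision or power for OS. Its only design figures concern ORR. Exact binomial calculation of the two-stage rule (stop at 5 or fewer or 11 or more of 28; otherwise success at 17 or more of 56) gives power 0.8055 against the stated 80.6%, and type I error 0.0483 against the stated 0.048. They reproduce and do not depend on the OS origin.

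**Inputs for the OS check**

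- Longest gap: 28 days (Section 5; the synopsis gives the same limit as 4 weeks). The start of Screening is taken as the earliest enrolment date.
- Intermediate gap: 10 days. Section 3.1, inclusion criterion 10, requires adequate organ function to be confirmed within 10 days of initiating treatment, so enrolment that follows confirmed eligibility would be no further than that from first dose.
- Shortest gap: 0 days, if enrolment means first dose.
- Median OS from first dose: the protocol assumes none. Section 1.1 gives 13 months, counted from the appearance of metastatic disease. It is used here as an illustration, with a range of 6 to 24 months as an assumption.
- Shape: exponential, also an assumption.

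**Formula.** With median M months and a gap of d days, 12-month OS reads S(d) = exp[−ln 2 × (12 − d/30.44)/M]. The overstatement is S(d) − S(0).

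**Results at M = 13** (monthly hazard ln 2/13 = 0.0533):

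- d = 0: exp(−0.0533 × 12) = 52.7%.
- d = 10: 10/30.44 = 0.329 months; 0.5274 × (exp(0.0175) − 1) = 0.0093, or +0.9 points.
- d = 14: 0.460 months; +1.3 points.
- d = 28: 0.920 months; 0.5274 × (exp(0.0490) − 1) = 0.0265, or +2.7 points, giving 55.4%.
- Gaps spread evenly over 0 to 28 days: +1.3 points on average.

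**Sensitivity to the median.** A 28-day gap adds 1.9 to 2.9 points over medians of 6 to 24 months, with the largest value near 8 months.

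**Scale.** With 56 patients and no censoring before 12 months, the 95% half-width is 1.96 × √(0.527 × 0.473/56) = 13.1 points. With 28 patients it is 18.5 points. The worst case of 2.65 points equals 0.0265 × 56 ≈ 1.5 patients, or 2.65/6.67 ≈ 0.4 of a standard error.

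**The case against.** The strongest reply is that the protocol leans towards a late enrolment date. Section 6.5 says when a patient number is allocated, not that allocation is enrolment. Numbers are given in Screening after consent, which includes patients who later fail screening, whereas the synopsis separates about 75 screened from up to 56 eligible and evaluable patients. Section 10.3 only puts consent before enrolment, which is true on any reading. Section 8.2.1 and the First Patient In definition in Section 8.6 point towards first dose. All of this stands. A reader might infer that OS is inflated by 28 days of guaranteed survival; the documents do not support that as the expected case. It requires enrolment at the start of Screening and every patient using the full window.

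A second reply is that fixing the calendar date is ordinary work for the statistical analysis plan, and that different origins for OS and PFS are not in themselves a contradiction. That is fair as far as it goes. But the protocol has already fixed the OS origin, with a term it does not date, alongside an analysis set conditioned on a later event. A SAP could only interpret or depart from that text.

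A third reply is that the effect is lost in the noise. This is right about size, and the half-widths above are if anything too narrow: the final analysis comes once the last patient has had the potential for 24 weeks of follow-up, so later entrants still alive would be censored before 12 months. It affects severity, not whether the wording should be repaired.

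A reader might also infer that PFS and duration of response are overstated because censoring is at the last clinical evaluation rather than the last scan. The documents do not establish this. Sections 5.3.10 and 8.5 require imaging until confirmed progression whatever the reason for stopping treatment, and telephone contact is provided for survival status (Section 5.1.1, Follow-Up). Any sizeable bias would rest on an assumed rate of patients who stop imaging.

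**Conclusion.** The point holds as a minor one. The OS origin is undated and differs from the PFS origin in the same section. Because the efficacy set requires a dose, any gap before first dose can only raise 12-month OS. With exponential survival and a 13-month median, the overstatement is 0 if enrolment means first dose, about 0.9 points for a 10-day gap, and at most 2.7 points for a full 28-day gap in every patient. The lower part of this range is more plausible, given how the protocol mostly uses the word. The actual gap is not known from the document, and the 13-month median is borrowed from a different starting point.

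The endpoint is secondary and descriptive, so no decision rule changes: the ORR analysis, the interim and final boundaries, type I error and power are all unaffected.

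**What to change.** In Section 8.12.2.3, measure OS from the date of first dose, as is already done for PFS. Alternatively, keep the present term and define the date of enrolment as the date of first dose.

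This is a one-sentence change using a date that PFS already needs. It alters no visit, procedure, sample size or boundary. The only cost is that reported 12-month OS may be slightly lower, by 0 to 2.7 points under the assumptions above.
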